7.2.4 Unanticipated Problems Involving Risks to Subject or Others

A UPIRSO is a type of SAE that includes events that meet ALL of the following criteria:

- Is *unanticipated* in terms of nature, severity, or frequency
- Places the research subject or others at a different or *greater risk of harm*
- Is deemed to be *at least possibly related* to participation in the study.

7.3 Adverse Event Reporting

7.3.1 Routine Reporting

All routine adverse events, such as those that are expected, or are unlikely or definitely not related to study participation, are to be reported on the appropriate eCRF according to the time intervals noted in the appendices. Routine AEs will be reviewed by the Data Monitoring Committee (DMC) according to the study's phase and risk level, as outlined in the DSMP.

7.3.2 Determining if Expedited Reporting is Required

This includes all events that occur within 30 days of the last dose of protocol treatment, unless definitely attributable to new anti-cancer treatment and NOT study treatment. Any event that occurs more than 30 days after the last dose of treatment and is attributed (possibly, probably, or definitely) to the agent(s) must also be reported accordingly.

- 1) Identify the type of adverse event using the NCI CTCAE v 4.03.
- 2) Grade the adverse event using the NCI CTCAE v 4.03.
- 3) Determine whether the adverse event is related to the protocol therapy. Attribution categories are as follows:
 - Definite: AE is clearly related to the study treatment.
 - Probable: AE is likely related to the study treatment.
 - Possible: AE may be related to the study treatment.
 - Unlikely: AE not likely to be related to the study treatment.
 - Unrelated: AE is clearly NOT related to the study treatment.
- 4) Determine the prior experience of the adverse event. Expected events are those that have been previously identified as resulting from administration of the agent. An adverse event is considered unexpected, for expedited reporting purposes only, when either the type of event or the severity of the event is not listed in:
 - the current protocol
 - the drug package insert
 - the current Investigator's Brochure

7.3.3 Expedited Reporting of SAEs/Other Events

7.3.3.1 Reporting to the Northwestern University QAM/DMC

All SAEs must be reported to the assigned QAM within 24 hours of becoming aware of the event. Completion of the NU CRO SAE Form is required.

The completed form should assess whether or not the event qualifies as a UPIRSO. The report should also include:

- Protocol description and number(s)
- The patient's identification number
- A description of the event, severity, treatment, and outcome (if known)
- Supportive laboratory results and diagnostics
- The hospital discharge summary (if available/applicable)

All SAEs will be reported to, and reviewed by, the DMC at their next meeting.

7.3.3.2 Reporting to the Northwestern University IRB

The following information pertains to the responsibilities of the lead site (Northwestern University). Additional participating sites should follow their local IRB guidelines for reporting to their local IRBs.

- Any death of an NU subject that is unanticipated in nature and at least possibly related to study participation will be promptly reported to the NU IRB within 24 hours of notification.
- Any death of an NU subject that is actively on study treatment (regardless of whether or not the event is possibly related to study treatment)
- Any death of a non-NU subject that is unanticipated and at least possibly related and any other UPIRSOs will be reported to the NU IRB within 5 working days of notification.

- All other deaths of NU subjects not previously reported, other non-NU subject deaths that were unanticipated and unrelated, and any other SAEs that were not previously reported as UPIRSOs will be reported to the NU IRB at the time of annual continuing review.

7.3.3.3 Reporting to the FDA

All reporting to the FDA will be completed by the Northwestern Quality Assurance (QA) department.

The FDA will be notified within 7 calendar days of any SAE that is associated with study treatment, is unexpected, and is fatal or life-threatening.

The FDA will be notified within 15 calendar days of any SAE that is associated with the study treatment, unexpected, and serious but *not fatal or life-threatening*. This includes any previous SAEs that were not initially deemed reportable, but are later determined to meet the criteria for reporting (i.e. by the DMC).

All other SAEs will be reported on an annual basis as part of the annual FDA report.

7.3.3.4 Reporting to Novartis

(NOTE: As of the 2nd March 2015, Novartis has taken over the pharmacovigilance activities.)

The principal investigator has the obligation to report all serious adverse events to Novartis Pharmaceuticals Drug Safety and Epidemiology Department (DS&E)

All events reported to the FDA by the investigator are to be filed utilizing the Form FDA 3500A (MedWatch Form).

To ensure patient safety, every SAE, regardless of suspected causality, occurring

- after the patient has provided informed consent and until at least 30 days after the patient has stopped study treatment/participation
- after protocol-specified procedures begin (e.g., placebo run-in, washout period, double-blind treatment, etc.) and 30 days after the patient has stopped study treatment
- after the start of any period in which the study protocol interferes with the standard medical treatment given to a patient (e.g., treatment withdrawal during washout period, change in treatment to a fixed dose of concomitant medication) and until 30 days after the patient has stopped study treatment

All Events must be reported to Novartis within 24 hours of learning of its occurrence. Information about all SAEs is collected and recorded on a Serious Adverse Event Report Form; all applicable sections of the form must be completed in order to provide a clinically thorough report. The investigator must assess and record the relationship of each SAE to each specific study treatment (if there is more than one study treatment), complete the SAE Report Form in English, and send the completed, signed form by fax to ([contact]) within 24 hours to the oncology Novartis DS&E department with the provided FAX cover sheets

(available as stand-alone documents) Novartis Study Code (CPZP034BUS52T) must be on the SAE coversheet. Should the designated SAE Fax # be non-functional please send SAEs to the designated SAE mailbox: [contact]. This includes serious, related, labeled (expected) and serious, related, unlabeled (unexpected) adverse experiences. All deaths during treatment or within 30 days following completion of active protocol therapy must be reported within 5 working days.

Any SAEs experienced after this 30 days period should only be reported to Novartis if the investigator suspects a causal relationship to the study drug. Recurrent episodes, complications, or progression of the initial SAE must be reported as follow-up to the original episode within 24 hours of the investigator receiving the follow-up information. A SAE occurring at a different time interval or otherwise considered completely unrelated to a previously reported one should be reported separately as a new event. The end date of the first event must be provided.

The original copy of the SAE Report and the fax confirmation sheet will be kept per local standard operating procedures.

Follow-up information is sent to the same fax number as the original SAE Report Form was sent, using a new fax cover sheet, stating that this is a follow-up to the previously reported SAE, and giving the date of the original report. Each re-occurrence, complication, or progression of the original event should be reported as a follow-up to that event regardless of when it occurs. The follow-up information should describe whether the event has resolved or continues, if and how it was treated, whether the blind was broken or not (if applicable), and whether the patient continued or withdrew from study participation.

If the SAE is not previously documented in the Pazopanib Investigator Brochure or Package Insert (new occurrence) and is thought to be related to the Novartis study drug, a DS&E associate may urgently require further information from the investigator for Health Authority reporting. Novartis may need to issue an Investigator Notification (IN), to inform all investigators involved in any study with the same drug that this SAE has been reported. Suspected Unexpected Serious Adverse Reactions (SUSARs) will be collected and reported to the competent authorities and relevant ethics committees in accordance with Directive 2001/20/EC or as per national regulatory requirements in participating countries.

To ensure patient safety, each pregnancy occurring while the patient is on study treatment must be reported to Novartis within 24 hours of learning of its occurrence.

8.0 DRUG INFORMATION

8.1 Topotecan

8.1.1 Other names: HYCAMTIN (Topotecan hydrochloride)

8.1.2 Classification - type of agent: Topotecan is a topoisomerase 1 inhibitor.

- 8.1.3 Mode of action:** The anti-tumor activity of topotecan involves the inhibition of topoisomerase-I, an enzyme intimately involved in DNA replication as it relieves the torsional strain introduced ahead of the moving replication fork. Topotecan inhibits topoisomerase-I by stabilizing the covalent complex of enzyme and strand-cleaved DNA which is an intermediate of the catalytic mechanism. The cellular sequela of inhibition of topoisomerase-I by topotecan is the induction of protein-associated DNA single-strand breaks.
- 8.1.4 Storage and stability:** Store refrigerated 2° to 8°C (36° to 46°F). Store the bottles protected from light in the original outer cartons.
- 8.1.5 Protocol dose specifics:** 8 milligrams orally on day 1, 8, 15 of a 28 day cycle. Drug to be taken with or without food.
- 8.1.6 Preparation:** No preparation is required.
- 8.1.7 Route of administration for this study:** Oral (by mouth)
- 8.1.8 Incompatibilities:** As with other myelosuppressive cytotoxic agents, greater myelosuppression is likely to be seen when topotecan is used in combination with other cytotoxic agents (e.g. paclitaxel or etoposide) thereby necessitating dose reduction. However, in combining with platinum agents (e.g. cisplatin or carboplatin), there is a distinct sequence-dependent interaction depending on whether the platinum agent is given on day 1 or 5 of the topotecan dosing. If the platinum agent is given on day 1 of the topotecan dosing, lower doses of each agent must be given compared to the doses which can be given if the platinum agent is given on day 5 of the topotecan dosing. When topotecan (0.75 mg/m²/day for 5 consecutive days) and cisplatin (60 mg/m²/day on Day 1) were administered intravenously in 13 patients with ovarian cancer, mean topotecan plasma clearance on Day 5 was slightly reduced compared to values on Day 1. As a result, systemic exposure of total topotecan, as measured by AUC and C_{max}, on Day 5 were increased by 12% (95% CI; 2%, 24%) and 23% (95% CI; -7%, 63%), respectively. No pharmacokinetic data are available following topotecan (0.75 mg/m²/day for 3 consecutive days) and cisplatin (50 mg/m²/day on Day 1) in patients with cervical cancer.

When oral topotecan was combined with cisplatin in a randomized Phase 3 study in chemotherapy-naïve, extensive disease, small cell lung cancer patients, the regimen of oral topotecan (1.7 mg/m²/d for 5 days) with i.v. cisplatin (60 mg/m² on day 5) was selected.

Topotecan is a substrate for both ABCG2 (BCRP) and ABCB1 (P-glycoprotein). Inhibitors of ABCB1 and ABCG2 (eg. elacridar) administered with oral topotecan increased topotecan exposure. The effect of elacridar on the pharmacokinetics of intravenous topotecan was much less than the effect on oral topotecan. Cyclosporin A (an inhibitor of ABCB1, ABCC1 [MRP-1], and CYP3A4) with oral topotecan increased topotecan AUC.

Patients should be carefully monitored for adverse events when oral topotecan is administered with a drug known to inhibit ABCG2 or ABCB1

The pharmacokinetics of topotecan after oral administration were generally Unchanged when coadministered with ranitidine.

NOTE: Refer to Appendix B for oral topotecan drug interactions.

8.1.9 Availability & Supply: Please complete the drug order form located on the protocol page in NOTIS. This form includes directions for ordering.

8.1.10 Side effects

Please refer to current IB for details and a complete list of side-effects.

8.1.11 Nursing implications

Bone Marrow Suppression

Inform patients that topotecan decreases blood cell counts such as white blood cells, platelets, and red blood cells. Instruct patients to notify their healthcare provider promptly for fever or other signs of infection such as chills, cough, or burning pain on urination. Advise patients that frequent blood tests will be performed while taking topotecan to monitor for bone marrow suppression.

Embryofetal Toxicity

Advise patients on pregnancy planning and prevention. Advise females of reproductive potential to use highly effective contraception during treatment and for 1 month following treatment with topotecan.

Advise males with a female sexual partner of reproductive potential to use effective contraception during and for 3 months after treatment.

Nursing Mothers

Advise patients to discontinue nursing during treatment with topotecan.

Infertility

Advise male and female patients of the potential risk for impaired fertility and possible family planning options.

Diarrhea

Inform patients that topotecan capsules cause diarrhea which may be severe and life-threatening. Instruct patients how to manage and/or prevent diarrhea and to inform their physician if severe diarrhea occurs during treatment with topotecan capsules.

8.1.12 Return and Retention of Study Drug: Unused or defective drug will be destroyed. Sponsor Novartis should be notified of this action.

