| Hemoglobin ^a | ≥9 g/dL (5.6 mmol/L) |
| Platelets ^a | ≥100 X 10 ⁹ /L |
| Prothrombin time (PT) or international normalized ratio (INR) ^b | ≤1.2 X ULN |
| Activated partial thromboplastin time (aPTT) | ≤1.2 X ULN |
| Hepatic | |
| Total bilirubin | ≤1.5 X ULN |
| Alanine amino transferase (ALT) and Aspartate aminotransferase (AST) ^c | ≤2.5 X ULN |
| Renal | |
| Serum creatinine | ≤1.5 mg/dL (133 μmol/L) |
| OR , if >1.5 mg/dL: Calculated creatinine clearance (Cl _{CR}) | ≥50 mL/min |
| Urine Protein to Creatinine Ratio (UPC;) ^d | <1 |
| , 24-hour urine protein, if required ^d | <1g |

- a. Subjects may not have had a transfusion within 7 days of screening assessment.
- b. Subjects receiving anticoagulant therapy are eligible if their INR is stable and within the recommended range for the desired level of anticoagulation.
- c. Concomitant elevations in bilirubin and AST/ALT above 1.0 x ULN (upper limit of normal) are not permitted.
- d. If UPC ≥1, then a 24-hour urine protein must be assessed. Subjects must have a 24-hour urine protein value <1 g to be eligible. Use of urine dipstick for renal function assessment is not acceptable.

3.1.9 Females of child-bearing potential (FOCBP) and males must agree to use adequate contraception (see Section 4.3.12) prior to study entry, for the duration of study participation, and for 30 days following completion of therapy. Should a female patient become pregnant or suspect she is pregnant while participating in this study, she should inform her treating physician immediately.

NOTE: A FOCBP is *any woman* (regardless of sexual orientation, having undergone a tubal ligation, or remaining celibate by choice) who meets the following criteria:

- *Has not* undergone a hysterectomy or bilateral oophorectomy
- *Has had* menses at any time in the preceding 12 consecutive months (and therefore has not been naturally postmenopausal for > 12 months)

3.1.10 FOCBP must have a negative pregnancy test within 7 days prior to registration on study.

NOTE: Female patients who are lactating should discontinue nursing prior to the first dose of study drug and should refrain from nursing throughout

the treatment period and for 14 days following the last dose of study drug

3.1.11 Are able to swallow and retain oral tablets.

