- c. If patient has completed 12 weeks of combination protocol therapy, and one protocol agent should be stopped per the above table, patient may be able to continue single agent therapy patient is deriving benefit and if approved by PI and QAM. This is based on how combination therapy would be administered outside of a clinical trial setting.
- d. Dose modifications should only be made after patient is given adequate supportive care.

Dose Modifications and Management of Liver toxicity

Recommendations for pazopanib dose interruptions/modifications in case of liver-related treatment-emergent AEs are provided in Table III. As a general rule, since many subjects are taking multiple concurrent medications, it is critical to (a) do a thorough evaluation of the subject’s concurrent medications (and ensure all are recorded in appropriate forms) , and (b) identify and discontinue those with known hepatotoxicity and replace with a non-hepatotoxic equivalent for the same indication if necessary. Record alcohol use on appropriate forms. Liver dysfunction must be fully evaluated even if clinical signs and symptoms indicate progression of liver tumor lesions. Imaging studies must be obtained to document potential progression of malignancy.

Table II Guidelines for Management of Treatment Emergent Hepatotoxicity

| Event | Dose Modification Algorithms |
|---|--|
| (A). ALT of ≤ 3.0 x ULN | Continue pazopanib and topotecan at current dose with full panel LFTs ^a monitored as per protocol. |
| (B). ALT >3.0 x ULN to ≤8.0 x ULN without bilirubin elevation (defined as total bilirubin ^b <2.0 x ULN or direct bilirubin ≤35%) and without hypersensitivity symptoms (e.g., fever, rash) | Liver Event Monitoring Criteria: (1) Continue pazopanib and topotecan at current dose levels. (2) Monitor subject closely for clinical signs and symptoms; perform full panel LFTs ^a weekly or more frequently if clinically indicated until ALT/AST is reduced to Grade 1. Recurrence – Liver Event Stopping Criteria^c: Discontinue protocol treatment permanently and monitor subject closely for clinical signs and symptoms; perform full panel LFTs ^a weekly or more frequently if clinically indicated until ALT/AST is reduced to Grade 1 or baseline. |

| | |
|---|---|

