4.3.1 Pregnancy/Lactation/Contraception

Pre-clinical studies in animals have shown reproductive toxicity. If the patient becomes pregnant while receiving pazopanib or topotecan, the potential hazard to the fetus should be explained to the patient. Women of childbearing potential should be

advised to avoid becoming pregnant while receiving treatment with pazopanib or topotecan. Pazopanib or topotecan should not be used during pregnancy or lactation.

Acceptable contraception methods, when used consistently and in accordance with both the product label and instructions of the physician are as follows:

- Complete abstinence from sexual intercourse during duration and treatment and for at least 30 days after the last dose of investigational product.
- Oral contraceptive, either combined estrogen/progesterone or progesterone alone.
- Injectable progestogen.
- Implants of levonorgestrel.
- Estrogenic vaginal ring.
- Percutaneous contraceptive patches.
- Intrauterine device (IUD) or intrauterine system (IUS) with a documented failure rate of less than 1% per year.
- Male partner sterilization (vasectomy with documentation of azoospermia) prior to the female patient's entry into the study, and this male is the sole partner for that patient.
- Double barrier method: condom and an occlusive cap (diaphragm or cervical/vault caps) with a vaginal spermicidal agent (foam/gel/film/cream/suppository).

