If a patient is felt to be deriving benefit from the agents and is stable at the conclusion of the trial, patients are allowed to continue therapy with stable disease by RECIST 1.1. This will be based on discussion with the patient, the PI, and sponsor. It may be possible to continue both drugs at that point, assuming availability of agents and no change in the status regarding pazopanib or topotecan with respect to sarcomas.

A patient may be removed from therapy if, in the judgment of the investigator, general or specific changes in the patient's condition render the patient unacceptable for further treatment.

4.6 **Duration of Follow Up**

Patients with PD at end of treatment will be followed every 6 months for 2 years (or until death) for survival. Patients without PD at end of treatment will be followed every 6 months for 5 years (or until death) for survival and progression. Follow-up may occur over the phone. Patients who are removed from study treatment for toxicity should be followed until toxicity resolves to grade 1 or baseline.

4.7 **Removal of Subjects from Study Treatment and/or Study as a Whole**

Patients can be taken off the study treatment and/or study as a whole at any time at their own request, or they may be withdrawn at the discretion of the investigator for safety, behavioral or administrative reasons. The reason(s) for discontinuation must be clearly documented on the appropriate eCRF and may include:

- Patient voluntarily withdraws from treatment (follow-up permitted)
- Patient withdraws consent (no follow-up permitted)
- Patient is unable to comply with protocol requirements

- Patient demonstrates disease progression
- Patient experiences unacceptable toxicity
- Treating physician determines that continuation on the study would not be in the patient's best interest
- Patient becomes pregnant
- Patient develops a second malignancy that requires treatment which would interfere with this study
- Patient becomes lost to follow-up (LTF)

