- Women of childbearing potential should be advised of the potential hazard to the fetus and to avoid becoming pregnant.
- Gastrointestinal adverse reactions such as diarrhea, nausea, and vomiting have been reported with pazopanib. Patients should be advised how to manage diarrhea and to notify their healthcare provider if moderate to severe diarrhea occurs.
- Patients should be advised to inform their healthcare providers of all concomitant medications, vitamins, or dietary and herbal supplements.
- Patients should be advised that depigmentation of the hair or skin may occur during treatment with pazopanib.
- Patients should be advised to take pazopanib without food (at least 1 hour before or 2 hours after a meal).

8.2.12 Return and Retention of Study Drug: Unused or defective drug will be destroyed. Sponsor Novartis should be notified of this action.

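### Criterion 3.1.9 asks men for 30 days of contraception after therapy, while section 8.1.11 advises 3 months for men with a female partner of reproductive potential

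*Combined protocol and SAP*

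**What the plan says.** Four places in the protocol bear on the point.

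- **3.1.9 (Inclusion Criteria)** covers women of child-bearing potential and men together: "males must agree to use adequate contraception (see Section 4.3.12"). The commitment runs "prior to study entry, for the duration of study participation, and for 30 days following completion of therapy". No different period is given for men.
- **8.1.11 (Nursing implications, topotecan)** separates the sexes. Women are to "use highly effective contraception during treatment and for 1 month following treatment with topotecan". For men the instruction is: "Advise males with a female sexual partner of reproductive potential to use effective contraception during and for 3 months after treatment".
- **4.3.1 (Pregnancy/Lactation/Contraception)** lists acceptable methods. Its only duration is in the abstinence option: "for at least 30 days after the last dose of investigational product". It states no period for male patients.
- **8.2.11 (Nursing implications, pazopanib)** speaks only to women and gives no duration: "Women of childbearing potential should be advised of the potential hazard to the fetus and to avoid becoming pregnant".

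Two further provisions affect how the durations are counted. Section 4.6 sets follow-up after treatment, for example "Patients with PD at end of treatment will be followed every 6 months for 2 years (or until death) for survival"; patients without progression are followed for 5 years. Table I, footnote c in section 4.3 says that after 12 weeks of the combination, if one agent has to be stopped, the "patient may be able to continue single agent therapy", subject to benefit and to approval.

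**The concern.** Two operative sections give different post-treatment periods for the same men. The shorter one is in the eligibility criterion, which cannot be waived (section 3.0) and is confirmed on a signed checklist before registration (section 11.3). The longer one appears only as counselling advice in a drug-information section.

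The female periods match and only the male period differs. This would be consistent with one duration having been written into 3.1.9 for both sexes, although the documents do not say how it arose.

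What is at stake is the clarity of a safety rule. Section 4.3.1 reports reproductive toxicity in animal studies, without male-specific data, and every patient starts topotecan. A man who treats the explicit 30 days in the criterion as his whole obligation would stop contraception about two months before the protocol's own topotecan advice says he should. No statistical quantity is involved.

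**Working it through.** There is no design figure to reproduce. The check sets the durations side by side and measures the difference.

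**Step 1. Durations after therapy**

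| Group | 3.1.9 | 8.1.11 (topotecan) | 4.3.1 | 8.2.11 (pazopanib) |
|---|---|---|---|---|
| Women of child-bearing potential | 30 days | 1 month | 30 days or more, abstinence option only | no period |
| Men with a female partner of reproductive potential | 30 days | 3 months | no male-specific period | men not mentioned |
| Other men | 30 days | not addressed | no male-specific period | men not mentioned |

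Only the second row conflicts. The 3 months comes from the topotecan section alone.

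**Step 2. Size if both periods start on the same date**

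Three calendar months last 89 to 92 days, depending on the start date.

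- Difference: 89 − 30 = 59 days, to 92 − 30 = 62 days.
- Share covered by the 30 days: 30/92 = 33%, to 30/89 = 34%.

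**Step 3. Dependence on what study participation means**

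- If participation ends with treatment, the explicit commitment is 30 days and the difference is 59 to 62 days.
- If participation includes the 2- or 5-year follow-up of section 4.6, a man who stays in follow-up for at least 3 months is already covered and the difference is zero.
- Even on that second reading, a man who withdraws consent when treatment ends has no follow-up (section 4.7). For him the 30-day clause applies and the difference returns.

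**Step 4. Dependence on what treatment means in 8.1.11**

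Suppose a man takes pazopanib alone for *d* days after his last topotecan dose.

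- If treatment means all study treatment, both periods start at the last dose of either drug and the difference stays at 59 to 62 days for any *d*.
- If treatment means topotecan only, which is an inference, the difference is (89 to 92) − (*d* + 30). It reaches zero at *d* = 59 to 62 days.

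This matters for the remedy. A rule counting 3 months from the last topotecan dose only, with 30 days after the last dose of any study drug as a floor, would leave a man with more than about 60 days of pazopanib alone with only 30 days after his last dose. If 8.1.11 means all study treatment, that is less than it advises.

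**The case against.** The strongest reply is that the two texts can stand together. Criterion 3.1.9 sets what a man must agree to in order to enter; it neither caps contraception nor calls longer use unnecessary. A man who follows 8.1.11 satisfies both sections, and staff are already directed to give the longer advice. This stands. A reader might infer that the protocol limits men to 30 days, or that it lacks the longer safety instruction. The documents support neither: 30 days is a minimum commitment, and the 3-month instruction is present.

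The second reply is that study participation may include follow-up, which would cover the 3 months. The usual answer is that this leaves the 30-day clause almost nothing to do. That answer is not decisive, because section 4.7 separates leaving treatment from leaving the study and the clause would still serve patients who withdraw consent. The text is ambiguous, so the shortfall has to be stated conditionally.

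The third reply is that little can now change. The Amendment 10 entry in Appendix H records cohorts 1 and 3 as closed to accrual, and the Amendment 13 entry records the study as closed. Amending an entry criterion binds no new patient. This also stands, with one reservation: treatment continues until progression or unacceptable toxicity (section 4.1), so some men may still be on treatment or recently off it.

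A reader might also infer that men were told 30 days. The consent wording is not in the material available, so that cannot be concluded.

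**Conclusion.** The inconsistency is real and minor. For men with a female partner of reproductive potential, the explicit post-therapy commitment in 3.1.9 is about one third of the period advised in 8.1.11, a difference of 59 to 62 days, and no other section reconciles them. That size assumes that both periods start on the same date and that study participation does not include follow-up. It is smaller or zero if follow-up counts, or if the 3 months runs from the last topotecan dose in a man who goes on with pazopanib alone.

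Only men still on treatment or within 3 months of stopping can be affected. Their number is not given and could be zero. The defect is incomplete alignment between a criterion and the protocol's own advice. It does not touch the endpoint, the sample size or the analysis.

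**What to change.** 1. In 3.1.9 and 4.3.1, keep the existing requirement before entry and during participation, and keep 30 days after therapy for women of child-bearing potential and for other men. Add that men with a female partner of reproductive potential continue contraception for 3 months after the last dose of study treatment, in line with 8.1.11. Counting from the last dose of study treatment avoids shortening protection for a man who continues one agent alone.
2. Confirm that men still on treatment, or within 3 months of stopping, have been given the 3-month advice.
3. As a separate editorial correction, change the cross-reference in 3.1.9 from 4.3.12 to 4.3.1, where the contraception text is found.

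The cost is a wording addition in two sections and a short check with the sites. With accrual closed, the second step is the one that could still matter to a patient. No design or analysis change is needed.
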